5.2 PROCEDURES FOR ENROLLMENT OF ELIGIBLE PATIENTS

Only patients who fulfill all entry criteria are eligible for enrollment into the study. Once the screening process is complete, the site should complete the Eligibility form in the CRF for review by the Medical Monitor. Once the Medical Monitor confirms eligibility in the CRF, shipment of IP will be triggered.

5.3 SAFETY ASSESSMENTS

Safety assessments will be based on AEs, prior and concomitant medication use, vital signs, ECG, physical examination, and laboratory assessments (hematology, blood chemistry, and anti-

bertilimumab antibodies, etc.). Measurements of all safety parameters should be performed as described in the Schedule of Events (Appendix A) and the following sections.

5.3.1 Adverse Events (AEs)

Adverse events will be assessed by the investigator throughout the study. Any AE that occurs after the informed consent is signed by the patient will be recorded in the patients' medical files as well as on the appropriate CRF page. (See Section 5.3.4).

AEs should be checked at each visit and recorded. Patients should be instructed to report any new AE that occurs between scheduled visits.

AEs will be coded by Data Management using Medical Dictionary for Regulatory Activities (MedDRA®) version 17.0 or higher.

5.3.2 Prior and Concomitant Medications

Recording of concomitant medication use will be conducted at all study visits. All treatments used by patients within 90 days prior to screening should be recorded. Any dose modification of concomitant medications should be checked at each visit and recorded. There will be a separate CRF page specifically for the entry of oral corticosteroid therapy for bullous pemphigoid.

5.3.3 Vital Signs

Vital signs will be measured at all visits except for Visit 9 (Day 118) as indicated in the Schedule of Events (Appendix A). At treatment administration Visits 2 (Day 0), 3 (Day 14), and 4 (Day 28), vital signs will be taken pre-dose (any time prior to the initiation of treatment infusion), at the completion of treatment infusion (approximately 30 minutes following the initiation of treatment infusion), and approximately 2 hours following the initiation of treatment infusion. All vital signs are to be obtained prior to any biopsies, treatment infusion, or laboratory/PK sampling collection if these procedures are scheduled at the same visit.

Vital signs will include blood pressure, pulse rate and oral temperature after at least 5 minutes of rest. Significant findings which meet the definition of an AE must be recorded on the AE CRF module.

5.3.4 ECG

ECG will be performed at Screening and Visit 8 (Day 84) as indicated in Appendix A. ECGs should be obtained prior to any biopsies or laboratory/PK sampling collection if these procedures are scheduled at the same visit.

The patient should rest for at least 10 minutes before measurement is taken. The ECG will be evaluated by the investigator (signed and dated) and the printout should be kept in the source documentation file.

When potentially clinically significant findings are detected by the site investigator, a cardiologist should be consulted for a definitive interpretation and treatment, if necessary. The investigator and local cardiologist are responsible to determine whether the ECG findings are of clinical significance. Significant findings made after the informed consent is signed which meet the definition of an AE must be recorded on the AE CRF. All abnormalities will be closely monitored until stabilized or resolved.

5.3.5 Physical Examination

Physical examination will be performed at all study visits except for Visit 9 (Day 118) as indicated in the Schedule of Events (Appendix A). On treatment administration Visits 2 (Day 0), 3 (Day 14), and 4 (Day 28), a physical examination will be performed prior to the initiation of the treatment infusion. Height will be recorded at Visit 1 (screening) only.

Physical examination will include weight and height (at screening only) measurements, assessment of head, lungs, cardiovascular system, abdomen, musculoskeletal system, skin, lymph nodes, central nervous system and, where appropriate, other body systems as indicated in the study schedule.

Information about the physical examination must be recorded in the source documentation at the study site. Significant findings that are present prior to the start of study drug must be included in the Relevant Medical History/Current Medical Conditions CRF. Significant findings made after the start of study drug, which meet the definition of an AE, must be recorded on the AE CRF.

5.3.6 Infusion Reactions

Infusion reactions should be assessed on treatment administration Visits 2 (Day 0), 3 (Day 14), and 4 (Day 28) as indicated in the Schedule of Events (Appendix A). At these visits, evidence for infusion reactions will be evaluated at the completion of treatment infusion (approximately 30 minutes following the initiation of treatment infusion) and at 2 hours following the initiation of treatment infusion.

5.3.7 Safety Laboratory Assessments

Safety laboratory assessments will be performed according to the Schedule of Events (Appendix A).

Hematology and Biochemistry will be performed at all visits with the exception of Visits 6 (Day 56), 7 (Day 70), and 9 (Day 118) as indicated in the Schedule of Events (Appendix A). At treatment administration Visits 2 (Day 0), 3 (Day 14), and 4 (Day 28), these samples will be taken pre-dose (any time prior to the initiation of treatment infusion). For screening, hematology and chemistry will be evaluated locally and at a central laboratory for all other visits.

Serology will be evaluated locally only at Screening.

Pregnancy will be evaluated locally by serum at Screening and locally by urine testing at all other visits with the exception of Visits 6 (Day 56) and 7 (Day 70).

Anti-bertilimumab antibodies will be evaluated at all visits with the exception of screening and Visit 9 (Day 118). At treatment administration Visits 2 (Day 0), 3 (Day 14), and 4 (Day 28), antibertilumamb samples will be collected pre-dose (any time prior to the initiation of treatment infusion). Anti-bertilumamb antibodies will be evaluated centrally.

The following parameters will be tested for each assessment:

Evaluations Parameters

Hematology Hematocrit, hemoglobin, platelet count, red blood cell count, reticulocytes, white

blood cell count with differential count, monocytes

Biochemistry Alanine aminotransferase, alkaline phosphatase, aspartate aminotransferase,

calcium, cholesterol, creatinine, gamma-glutamyl transferase, glucose, potassium,

sodium, total bilirubin, triglycerides, urea or BUN

Immunology Anti-bertilimumab antibodies

Pregnancy test Serum β-hCG

Urine β-hCG

Serology For HBV (HBsAg or HBcAb), HCV (HCV Ab), HIV (HIV1/2 Ab), CMV (IgM)

All laboratory tests with abnormal values which are considered clinically significant and are detected after the informed consent is signed will be repeated as clinically indicated until the values return to normal, or until the etiology has been determined and the condition considered stable. Abnormal laboratory test results that are considered clinically important by the investigator will be reported as an AE in the AE CRF.

Laboratory results will be reported to the investigator who will review abnormal laboratory findings for clinical significance. The investigator will note any laboratory test results of clinical concern, or values that are outside normal ranges and provide details of the relationship to investigational product and the action taken. If a change in a laboratory value represents a medical condition, the medical condition will be listed in the AE CRF page. If no correlation is determined, the direction of change (increase or decrease) in addition to the actual value will be recorded.

Refer to the Laboratory Manual for more details.

5.3.7.1 Semen analysis testing

Semen testing will be performed at Visits 2 (Day 0), 3 (Day 14), 4 (Day 28). Visit 9 (Day 118) will only be required if any results from the previous visits are abnormal compared to pre-dose Visit 2 (Day 0). At treatment administration Visits 2 (Day 0), 3 (Day 14), and 4 (Day 28), semen testing will be performed pre-dose (any time within 48 hours prior to the initiation of treatment infusion), and at the completion of treatment infusion (approximately 30 minutes following the initiation) or as close to this time as possible.

Semen analysis will be performed on all male patients participating in this study with the exception of the following:

- Infertile males
- Patients with religious constraints that prevent them from providing semen samples

5.3.7.2 Tuberculosis Evaluation

An evaluation for active/latent tuberculosis will be performed at Screening as indicated in the Schedule of Events (Appendix A). The evaluation will be performed locally either clinically, radiographically, or by laboratory (i.e., PPD, X-ray, or Quantiferon Gold). Quantiferon Gold testing will also be available centrally as an option, where applicable.

5.4 EFFICACY ASSESSMENTS

5.4.1 Bullous Pemphigoid Disease Area Index (BPDAI)

The BPDAI (See Appendix D) will be completed at all visits with the exception of Visit 9 (Day 118) as indicated in the Schedule of Events (Appendix A). At treatment administration Visits 2 (Day 0), 3 (Day 14), and 4 (Day 28), the BPDAI should be completed pre-dose (any time prior the initiation of treatment infusion). In screening, the BPDAI should be performed, if possible, prior to commencement of corticosteroid regimen.

The BPDAI Pruritus Component Visual Analogue Scale (VAS) will be completed by the patient or their legally authorized representative and all other sections for the BPDAI will be completed by the investigator. Patients and investigators will be asked to complete their respective sections on the corresponding worksheets, which will serve as source documentation for this measurement. The study source documents should reflect any issues that may have occurred during completion.

5.4.2 Assessment of Lesion Healing

The assessment of lesion healing will be completed at all visits with the exception of Visit 9 (Day 118) as indicated in the Schedule of Events (Appendix A). As part of the assessment for control of disease activity, one of the efficacy endpoints, investigators will be asked to document whether established lesions have started to heal.

5.4.3 Autoimmune Bullous Disease Quality of Life (ABQOL)

The ABQOL (See Appendix E) will be completed at all visits with the exception of Visit 9 (Day118) as indicated in the Schedule of Events (Appendix A). At treatment administration Visits 2 (Day 0), 3 (Day 14), and 4 (Day 28), the ABQOL should be completed pre-dose (any time prior the initiation of treatment infusion). In screening, the ABQOL should be completed, if possible, prior to commencement of corticosteroid regimen.

Patients or their legally authorized representative will be asked to complete the ABQOL on the worksheets, which will serve as source documentation for this measurement. The study source documents should reflect any issues that may have occurred during completion.

5.4.4 Photography

Photographs will be taken at all visits with the exception of Visit 9 (Day 118) as indicated in the Schedule of Events (Appendix A). At treatment administration Visits 2 (Day 0), 3 (Day 14), and 4 (Day 28), the photographs should be completed pre-dose (any time prior to the initiation of treatment infusion). In screening, the photography should be conducted, if possible, prior to commencement of corticosteroid regimen.

Refer to the Photography User Manual for more details.

5.5 PHARMACOKINETIC (PK) ASSESSMENTS

PK will be measured at all visits with the exception of Screening and Visit 9 (Day 118) as indicated in the Schedule of Events (Appendix A). At treatment administration Visits 2 (Day 0), 3 (Day 14), and 4 (Day 28), PK samples will be collected pre-dose (within 30 minutes prior to the initiation of treatment infusion), at the completion of treatment infusion (approximately 30 minutes following

the initiation of treatment infusion), and 2 hours following the initiation of treatment infusion. All PK samples should be collected after vital signs, physical examination, and ECG if these procedures are scheduled at the same visit.

PK outcome refers to study drug (bertilimumab) concentration in the serum. PK parameters may include:

C_{max} Maximum bertilimumab serum concentration

 T_{max} Time to C_{max} (peak exposure)

C_{avg} Average bertilimumab serum concentration

C_{min} Minimum bertilimumab serum concentration

 λ_z Elimination rate constant

 $t_{1/2}$ Elimination half-life, calculated as $0.693/\lambda_z$

Additional PK parameters may be calculated if deemed necessary.

Refer to the Laboratory Manual for more details.

5.6 PHARMACODYNAMIC (PD) ASSESSMENTS

5.6.1 Eosinophil Count in Biopsy Tissue

Eosinophil count in the skin biopsy tissue will be evaluated at Screening and Visit 5 (Day 42) as indicated in the Schedule of Events (Appendix A). This assessment will be evaluated centrally, where feasible.

This biopsy should be collected using a 4-6 mm punch at the edge of a lesion or blister and should include some adjacent unaffected skin, as the sample must contain intact epithelium. At Screening and at Visit 5 (Day 42), the same biopsy sample will be used to determine eosinophil count and the eosinophil make up of the inflammatory infiltrate with hematoxylin and eosin staining. The Visit 5 (Day 42) biopsy should be taken from approximately the same location as the one from Screening.

Refer to the Laboratory Manual for more details.

5.6.2 Eosinophil count in Blood

Eosinophil count in the blood will be evaluated as part of the hematology assessment at all visits with the exception of Visits 6 (Day 56), 7 (Day 70), and 9 (Day 118) as indicated in the Schedule of Events (Appendix A). This assessment will be evaluated centrally.

5.6.3 BP180 and BP230 Autoantibodies

BP180 and BP230 autoantibodies will be evaluated at all visits with the exception of Visit 9 (Day 118) as indicated in the Schedule of Events (Appendix A). This assessment will be evaluated centrally, where feasible.

Refer to the Laboratory Manual for more details.

5.6.4 Serum Level of Eotaxin-1

Serum levels of eotaxin-1 will be evaluated at all visits except Screening and Visit 9 (Day 118) as indicated in the Schedule of Events (Appendix A). This assessment will be evaluated centrally.

Refer to the Laboratory Manual for more details.

5.7 OTHER ASSESSMENTS

5.7.1 Bullous Pemphigoid Diagnosis

In order to diagnose patients with bullous pemphigoid for this study, the following assessments will be performed at Screening. However, if any of these assessments have been performed within 4 weeks prior to screening, the assessment will not have to be repeated. With the exception of the clinical evaluation, all of these assessments, if performed during screening, will be evaluated at the central clinical laboratory, where feasible. Though all assessments have to be performed, ultimate determination of a positive diagnosis is up to the investigator.

5.7.1.1 Clinical Evaluation

Clinical evaluation of the patient for diagnosing bullous pemphigoid will be performed at Screening.

5.7.1.2 Hematoxylin and Eosin (H&E) Staining

H&E of the skin biopsy tissue will be evaluated at Screening and Visit 5 as indicated in the Schedule of Events (Appendix A).

H&E will be performed in order to determine the eosinophil make up of the inflammatory infiltrate.

This biopsy should be taken using a 4-6 mm punch at the edge of a lesion or blister and should include some adjacent unaffected skin as the sample must contain intact epithelium. At Screening and Visit 5 the same biopsy sample will be used to determine eosinophil count and the eosinophil make-up of the inflammatory infiltrate with hematoxylin and eosin staining.

See the Laboratory Manual for more details.

5.7.1.3 Direct Immunofluorescence (DIF) and Salt Split Skin

DIF on salt split skin of skin biopsy tissue will be evaluated at Screening as indicated in the Schedule of Events (Appendix A).

DIF on salt split skin will be performed to check the linear deposition of IgG and/or C3 on the blister roof (epidermal side) as part of the diagnosis for bullous pemphigoid.

The biopsy should be taken using a 4-6mm punch of erythematous perilesional skin, approximately 0.5 to 1 cm away from a fresh blister. Avoid erosions, ulcers, and bullae while obtaining tissue adjacent to active lesions.

See the Laboratory Manual for more details.

5.7.1.4 BP180 and BP230 Autoantibodies

BP180 and BP230 autoantibodies will be evaluated at Screening as indicated in the Schedule of Events (Appendix A).

Patients will be tested for the presence of BP180 and BP230 autoantibodies. At Screening, the same sample will be used to test for BP180 and BP230 autoantibodies and IgG circulating autoantibodies with IIF.

See the Laboratory Manual for more details.

5.7.1.5 Indirect Immunofluorescence (IIF)

IIF of the patient's serum will be evaluated at Screening as indicated in the Schedule of Events (Appendix A).

IIF of the patient's serum will be performed to check for the presence of IgG circulating autoantibodies. At Screening, the same sample will be used to test for BP180 and BP230 autoantibodies and the IIF.

See the Laboratory Manual for more details.

5.7.2 Assessment of BP Severity

Moderate to extensive BP will be defined by the number of bullae and/or urticarial plaques that have appeared on 3 occasions during the screening period. The number of bullae and/or urticarial plaques can be monitored at the clinical site and recorded by the investigator or it can be reported by the patient or caregiver. The number of bullae and/or urticarial plaques should be documented on the Assessment of BP Severity form (see Appendix B). The assessment should be performed at approximately the same time each day.

5.7.3 Karnofsky Performance Status Scale

The Karnofsky Performance Status Scale, an assessment tool for functional impairment (Appendix C), will be evaluated at Screening as indicated in the Schedule of Events (Appendix A).

5.7.4 Biomarkers

Biomarker sample collection will be performed at Visit 2 (Day 0) and Visit 5 (Day 42) as indicated in the Schedule of Events (Appendix A). At Visit 2 (Day 0), biomarkers will be collected pre-dose (any time prior to the initiation of treatment infusion).

5.8 EARLY DISCONTINUATION STUDY VISIT

An early discontinuation study visit will be performed for patients who withdraw from the study for the reasons specified in Section 4.5.1.

All reasons for treatment discontinuation will be documented in the source documents as well as the CRF. Only one reason (the most severe) for early discontinuation should be recorded in the CRF. If one of the reasons for discontinuation is an AE – this should be chosen as the reason. Every effort should be made to follow-up these patients for resolution of the AE.

The required assessments that are to be performed during an early discontinuation visit are indicated in the Schedule of Events (Appendix A), but assessments may be added at the discretion of the investigator.

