1.3.1 Rationale for Dose Selection

Immune Pharmaceuticals has chosen to evaluate the 10 mg/kg IV dose of bertilimumab based on the following safety, pharmacokinetic and PD data:

- No safety concerns were identified in Study CAT-213-0101, in which subjects received a single IV bertilimumab dose of up to 10 mg/kg (corresponding to absolute doses of 570 to 770 mg in four patients), or in Study CAT-213-0103, in which patients received a single IV bertilimumab dose of up to 500 mg.
- The PD endpoint in Study CAT-213-0101, eotaxin-induced eosinophil shape change, was inhibited by serum in all subjects who received bertilimumab doses of 1 mg/kg and higher, with nearly 100% inhibition in the 5 mg/kg and 10 mg/kg dose groups. A shape change in eosinophils is considered a requisite process in chemotaxis, and can be taken as evidence of an impending migratory response. Maximum inhibition occurred at concentrations of ~40 μg/mL. At 35 days post-dose, high levels of inhibition were still observed despite low concentrations of bertilimumab, suggesting that the PD response was prolonged when compared with the bertilimumab plasma concentrations.
- In Study CAT-213-0101, after a single dose of 5 mg/kg, unbound bertilimumab had a mean half-life of 211 hours (CV% 30.5); the mean half-life after a single 10 mg/kg dose was 194 hours (CV% 27.1).
 - The data from this study also suggest dose proportionality in bertilimumab exposure between these two doses.
- No antibodies to bertilimumab were detected in any of the three previous single-dose clinical trials.

In the healthy volunteer and patient studies performed to date, bertilimumab doses up to 10 mg/kg have not been associated with any dose-related adverse effects.

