4.5 REMOVAL, REPLACEMENT, OR EARLY DISCONTINUATION OF PATIENTS FROM THERAPY OR ASSESSMENT

Patients are free to discontinue their participation in the study at any time and without prejudice to further treatment. The investigator must withdraw any patient from the study if that patient requests to be withdrawn, or if it is determined that continuing in the study would result in a significant safety risk to the patient. Withdrawn patients will not be replaced once treatment has been administered.

The following are examples of reasons why a patient's participation in this study may be discontinued:

- Patient withdraws consent
- Intolerable adverse event
- The investigator decides that continuing in the study would not be in the patient's best interest
- The patient is noncompliant with the protocol
- The patient becomes pregnant
- Upon the decision of relevant Regulatory Authorities and/or the Institutional Review Board/Independent Ethics Committee (IRB/IEC).

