4.5.1 Handling of Early Discontinuation

If a patient is withdrawn from the study, either at his or her request or at the investigator's discretion, or fails to return, every effort should be made to determine the reason. This information will be recorded on the patient's case report form (CRF). All patients who withdraw from the study prematurely, regardless of cause, should undergo Early Discontinuation Study Visit (see Section 5.8). It is important to obtain follow-up data for any patient withdrawn due to an AE or abnormal laboratory test finding. In any case, every effort must be made to undertake safety follow-up procedures.

Premature withdrawal may occur for any of the following reasons:

- Death
- Pregnancy
- AE
- Patient request
- Investigator request
- Sponsor request

Any serious AE (SAE) must be entered into the CRF and reported to the Sponsor or Sponsor's designee by email and/or fax within 24 hours and to the IRB/IEC according to site's regulations (for SAE notification procedures, refer to Section 7.4).

In the event of any AEs considered clinically significant by the investigator, patients will be provided with appropriate medical management until the outcome is determined or stabilized, according to the investigator's clinical judgment. All follow-up information will be recorded in the patient's CRF until the close of the study. Subsequent follow-up will be documented in the patient's personal file.

Patients who fail to respond to study treatment or experience a flare will be able to receive local standard-of-care at the investigator's discretion.

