Any new SAE that occurs up to 30 days after the study period and is considered related (possibly/probably) to the investigational product or study participation should be recorded and reported immediately.

A **life-threatening** adverse drug experience is any adverse event that places the patient, in the view of the investigator, at immediate risk of death from the reaction as it occurred, i.e., it does not include a reaction that, had it occurred in a more severe form, might have caused death.

Every attempt should be made to describe the AE/SAE in terms of a diagnosis. However, if an observed or reported sign or symptom is not considered a component of a specific disease or syndrome by the Investigator, it should be recorded as a separate AE/SAE on the eCRF. Once a clear diagnosis has been made, individual signs and symptoms shall not be recorded unless they represent atypical or extreme manifestations of the diagnosis, in which case they should be reported as separate events. If a clear diagnosis cannot be established, each sign and symptom must be recorded individually.

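### Stopping bertilimumab is not separated from leaving the study, so a patient who ends early has no scheduled collection of new safety events after one untimed visit

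*Protocol*

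**What the plan says.** Protocol section 4.5 gives "Intolerable adverse event" as one example of why participation may be discontinued. It requires withdrawal at the patient's request, or when continuing in the study would be a significant safety risk. That trigger is framed as continuing in the study, not as continuing infusions.

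Section 4.5.1 states: "All patients who withdraw from the study prematurely, regardless of cause, should undergo Early Discontinuation Study Visit". Section 5.8 repeats this: "An early discontinuation study visit will be performed for patients who withdraw from the study for the reasons specified in Section 4.5.1". Its next paragraph then asks for the reasons for treatment discontinuation, as if that were the same event. Appendix A has one Early Discontinuation column without a study day, and no contact after it.

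Some duties continue after withdrawal:

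- Section 4.5.1: "It is important to obtain follow-up data for any patient withdrawn due to an AE or abnormal laboratory test finding", and "In any case, every effort must be made to undertake safety follow-up procedures". Follow-up of clinically significant AEs goes into the CRF until the study closes.
- Section 5.8, for those leaving because of an AE: "Every effort should be made to follow-up these patients for resolution of the AE".
- Section 5.3.7: clinically significant abnormal laboratory tests are repeated until normal, or until explained and stable.
- Section 7.4: all AEs are followed to resolution or stabilization, with a defined exception.
- Section 7.2, for new events: "Any new SAE that occurs up to 30 days after the study period and is considered related (possibly/probably") to the product or to study participation is to be reported.

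Completers have visits to Day 84 and then calls with AE assessment at about Days 144 and 204 (protocol sections 3.0 and 5.11, Appendix A).

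The SAP safety population is everyone with at least one infusion (section 6.1). AEs and SAEs are tabulated as numbers and percentages of subjects (sections 9.3.1 and 9.3.2). Missing data are not imputed.

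**The concern.** Safety is the primary objective. Following a known AE is a different task from finding a new one. The continuing duties mostly concern events already recorded, or are best-effort duties with no schedule or duration. After the discontinuation visit, nothing scheduled would elicit a new non-serious AE or an SAE judged unrelated, and no further laboratory or antibody sample is planned.

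The protocol's own pharmacology suggests that the drug outlasts such a visit. Section 1.3.1 gives mean half-lives of 194 and 211 hours, and reports: "At 35 days post-dose, high levels of inhibition were still observed despite low concentrations of bertilimumab".

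In the analysis, a patient seen for one or two weeks after the last infusion counts in the AE denominators exactly like one seen for 56 days. Whatever happens to that patient later, and goes uncollected, appears as an absence of events.

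**Working it through.** **Inputs.** Infusions on Days 0, 14 and 28; Visit 8 on Day 84; calls at about Days 144 and 204; at most 15 patients (protocol synopsis, section 3.0, Appendix A). Half-lives are 194 h (10 mg/kg, CV 27.1%) and 211 h (5 mg/kg, CV 30.5%) from section 1.3.1. The timing of the discontinuation visit is not given, so 0, 7 and 14 days after the last infusion are assumed.

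**1. The plan's own figure.** Day 84 − Day 28 = 56 days, matching the stated follow-up of about 56 days. The last call is 204 − 28 = 176 days after the last infusion.

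**2. Scheduled contact after an early stop, against the completer's 56 days.** The third column assumes that the study period ends at the discontinuation visit, which the protocol does not say.

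| Discontinuation visit, days after last infusion (assumed) | Days short of 56 | End of 30-day related-SAE window, days after last infusion |
|---|---|---|
| 0 | 56 | 0 + 30 = 30 |
| 7 | 49 | 7 + 30 = 37 |
| 14 | 42 | 14 + 30 = 44 |

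On that assumption the window ends before day 35 only if the visit falls within 5 days of the last infusion. If the study period instead means the patient's planned course of about 204 days, the window is far longer, but there is still no scheduled contact to bring an event to light.

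**3. Drug remaining at the last scheduled sample.** Fraction = 2^(−t / half-life), assuming first-order decay after one dose.

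- 7 days (168 h): 2^(−168/194) = 0.549; 2^(−168/211) = 0.576.
- 14 days (336 h): 2^(−336/194) = 0.301 (0.19 to 0.39 over ±1 CV); 2^(−336/211) = 0.332 (0.20 to 0.43).
- 35 days (840 h): 2^(−840/194) = 0.050; 2^(−840/211) = 0.063.
- Five half-lives: 5 × 194 / 24 = 40.4 days; 5 × 211 / 24 = 44.0 days.

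A visit at 7 to 14 days is therefore made with roughly 30% to 58% of the drug still present. Completers' visits run past five half-lives on the mean figures.

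**4. Weight in the tables.** 1/15 = 6.7%; 2/15 = 13.3%. If a later event in one early leaver goes uncollected, a row that should read 1/15 (6.7%) reads 0/15.

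**5. Would the SAP show it?** Section 9.1 lists dropouts with time from consent to termination, not time since the last infusion. The exposure item in section 9.3.2 is the number of infusions. Section 8 derives a study duration, but no table uses it. Follow-up after the last infusion is not planned as an output.

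**6. What staying on schedule would give.** To Visit 8: 84, 70 or 56 days after the last infusion, for a patient who stops after the first (84 − 0), second (84 − 14) or third (84 − 28).

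**The case against.** The strongest reply is that follow-up does not end at the discontinuation visit. The duties in sections 4.5.1, 5.3.7, 5.8 and 7.4 are real, and the visit itself includes examination, vital signs, ECG, laboratory tests, antibodies and PK. This stands for events already known. It does not supply scheduled detection of new ones.

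A second reply is that the protocol never requires a patient who stops infusions to leave. Section 4.5 gives examples of when participation may end, so the fault is ambiguous wording rather than a rule. That is fair, but no alternative route is described, and section 5.8 treats the two events as one.

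Third, the SAP already tabulates the number of infusions and, separately, study completion and termination reasons. With listings of all CRF data, a reader could rebuild the rest for 15 patients. This lowers the cost of the fix, but it cannot recover events that were never collected.

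Three stronger readings are tempting and should not be drawn:

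- *Follow-up is shortest in those who tolerate the drug worst.* The single visit applies to every withdrawal whatever the cause, and those leaving for an AE carry more explicit follow-up duties than other leavers.
- *Every safety rate is biased downward.* A patient who stops for an AE is already in the all-AE numerator, and in the related-AE numerator if the event was judged related. Only later, additional events are at risk. Antibody results are summarised by visit on observed data, so a missing sample reduces that visit's n and dilutes no rate.
- *The drug acts for at least 35 days, so safety risk lasts that long.* The result comes from a single-dose test of eosinophil shape change, read at 35 days when concentrations were low. It is not a duration of clinical risk.

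**Conclusion.** The point holds as a gap in data collection for the primary objective. A patient who ends early, including for an AE, has one untimed visit and then no scheduled collection of new safety data. New related SAEs alone have a stated window, tied to an end date that is undefined for that patient. Compared with completers, 42 to 56 days of scheduled follow-up are lost if the visit falls 0 to 14 days after the last infusion; that range is an assumption. AE and SAE counts can be understated by later events in such patients, each worth 6.7% of a full 15. The documents do not say how many patients ended early, so the actual effect is unknown and could be nil. The half-life figures illustrate why the interval matters; the conclusion does not depend on them.

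**What to change.** **Protocol.** Reconcile sections 4.5, 4.5.1 and 5.8 so that stopping bertilimumab and withdrawing from the study are distinct. A patient who stops infusions without withdrawing consent to follow-up stays on the scheduled assessments to Visit 8 and the two calls. Use the discontinuation visit when the patient declines further visits. In that case, and if the patient agrees, collect AEs and SAEs by phone, regardless of causality, to 56 days after the last infusion. Define the end of the study period in section 7.2 for a patient who leaves.

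**SAP.** In the disposition table, show stopping infusions and study withdrawal as separate rows. List for each patient the days of follow-up since the last infusion, beside the AE tables.

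**Cost.** A short amendment, one extra disposition row and one listing. The visits and calls are already scheduled; the phone collection is a small addition. The downside is that some patients attend visits off drug. SAP section 7.4 mentions a decision taken after the study was completed, so the amendment may come too late for this trial. The SAP changes can still be made, and the wording can be carried into a later protocol. No rule on when treatment should stop is proposed.
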